2. Unstable clinical status
3. Noninvasive or invasive CV testing for CAD within 1 year. CV testing for CAD refers to any stress tests, invasive coronary angiography (ICA), and cCTA (including calcium scoring) only.
 - a) *Resting ECG, resting echocardiogram and resting CMR (MRI) are not exclusionary regardless of when they were performed.*
4. Lifetime history of known obstructive CAD (prior myocardial infarction, CABG or PCI, stenosis $\geq 50\%$), known EF $\leq 40\%$ or other moderate to severe valvular or congenital cardiac disease
5. Contraindications to cCTA including but not limited to creatinine clearance (GFR) < 45 ml/min as per most recent measurement taken within 90 days
6. Exceeds the site's weight or size limit for cCTA or cardiac catheterization
7. Any condition leading to possible inability to comply with the protocol procedures and follow-up
8. Any condition that might interfere with the study procedures or follow-up
9. Enrolled in an investigational trial that involves a non-approved cardiac drug or device which has not reached its primary endpoint
10. Life expectancy less than 2 years due to non-cardiovascular comorbidities

Screening visit (in-person)

Participant will be randomized to either the usual care arm or the precision evaluation arm within 14 days of screening.

At the screening visit, patients will undergo the following:

- Review consent form and have all questions appropriately answered.
- Provide consent by signing the Informed Consent Form
- Review of medical history
- Review of concomitant medications
- Pregnancy test (for females of child-bearing potential – those who have not been surgically sterilized or are not postmenopausal)
- Creatinine test (if not done in last 90 days)

Resting 12-lead ECG (optional, clinical care only) Assessment of CAD risk will be performed during screening to ensure eligibility. It will include:

- General medical history
- Cardiovascular risk factors and comorbidities as well as prior testing or events
- Physical exam
- Laboratory testing

The following major cardiac risk factors will be assessed:

- Age
- Sex
- BP/hypertension
- Diabetes
- Cholesterol (including low-density lipoprotein [LDL], high-density lipoprotein [HDL]), if available
- Smoking status
- Family history
- Sedentary life style
- Obesity (BMI, waist hip ratio)
- Cerebrovascular and peripheral arterial disease (PAD)
- Ankle brachial index (ABI)

V.B. Randomization and Enrollment

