4.2 Pre-specified Subgroup Analyses

4.2.1 Primary endpoint subgroup analyses

The following subgroup treatment/strategy comparisons will be conducted for the primary endpoint at 12 months as a forest plot with an interaction p-value.

1. Demographic and clinical subgroups

- Sex: Male/Female
- Age: <65, 65 to 74, \geq 75 years
- Race/ethnicity:
 - White/non-Hispanic vs. other
- Risk score:
 - Low vs. elevated (All Participants);
 - Low vs. elevated (excluding known obstructive atherosclerosis);
 - Above and below PRECISE median score

Risk score cut point based on the top 10% of low risk of the PROMISE Risk Score in the PROMISE cohort. Low Risk is defined as an absolute score >0.46 (see derivation in section 6.1 below).
- History of diabetes: Yes/No
- History of CAD/PAD/abnormal ABI: Yes/No
- Obesity: (BMI< 25, 25-30, >30)
- Geographic region: United States vs. Outside the United States

2. Intended first test is noninvasive vs. invasive
3. Symptoms and risk subgroups at presentation/randomization
 - Primary symptom presentation: 1) Typical Angina, 2) Atypical Pain, 3) Dyspnea, and 4) Non-Cardiac Pain/other
 - ESC modified Diamond-Forrester Pre Test Probability score (2019) with the population divided as <5% pretest probability, 5-15%, and $>15\%$.
 - Tertiles of ASCVD risk score
 - SAQ angina score at presentation: More frequent angina ($</= 80$) vs. Rare/absent angina (>80)

5. Population Treatment Assignment for Analysis

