5.3 Subgroups of Intention-To-Treat and Per-Protocol

Four treatment comparisons will be made.

- Including only Intention-To-Treat participants from the low risk strata
- Including only Intention-To-Treat participants from the elevated risk or known atherosclerosis strata
- Including only Per-Protocol participants from the low risk strata
- Including only Per-Protocol participants from the elevated risk or known atherosclerosis strata

6. Participant Randomization and Enrollment

Once a participant has consented to participate in the trial, participant information will be entered in the database. If a patient is a screen failure, the data that have been collected up until this point for the patient for screening purposes will be entered into the eCRF in the EDC system. No additional information will be collected after this point for such a patient.

Participants who meet all inclusion criteria and none of the exclusion criteria will be randomized in a ratio of 1:1 within a clinical center to either of the following 2 groups using an IXRS.

Precision care - precision care strategy

Usual care- usual care strategy

Randomization will be stratified by intended first test assuming usual care (invasive vs. noninvasive) and by classification as low vs. elevated risk by the PROMISE risk model (see derivation below in Section 6.1). For testing purposes, participants with known non-obstructive coronary atherosclerosis or plaque will be assigned to the elevated risk strata regardless of risk score. The randomization scheme within a clinical center will be carried out by the method of random permuted block design. Participants will be randomized to either the usual care arm or the precision evaluation arm within 14 days of screening. The following tables summarizes the strata:

Summary of Strata

Strata	First Test	Risk
1	Non-Invasive	Low Risk
2	Non-Invasive	Elevated Risk or Known Atherosclerosis
3	Invasive	Low Risk
4	Invasive	Elevated Risk or Known Atherosclerosis

Enrollment in the randomization strata of intended first test being noninvasive (vs. invasive testing or direct to catheterization) will be capped at 90% of the sample size.

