6.1 Risk Groups based on PROMISE Risk Score

To calculate the PROMISE risk score use the following table estimates based on the risk score paper (Fordyce, JAMA Cardiology 2017). The Promise Score is equal to $1/(1+\exp(\text{logit}))$.

Logit Equation= $\gamma_1 + \gamma_2 * \text{Age (Years)} + \gamma_3 * \text{Sex(female=1)} + \gamma_4 * \text{Caucasian/Non-Hispanic (no=1)} + \gamma_5 * \text{Tobacco(current or former=1)} + \gamma_6 * \text{Diabetes(yes=1)} + \gamma_7 * \text{Dyslipidemia(yes=1)} + \gamma_8 * \text{Family history of premature (<55 years)Coronary artery disease(yes=1)} + \gamma_9 * \text{hypertension(yes=1)} + \text{Symptoms unrelated to physical or mental stress (not related=1)} + \gamma_{11} * \text{Symptoms unrelated to physical or mental stress(unknown=1)} + \gamma_{12} * \text{HDL (mg/dL)}$

Logit Equation coefficients

		HDL is available	HDL is not available	
			Female	Male
Intercept	γ_1	-3.7524	-3.7524	-3.7524
Age (Years)	γ_2	0.0842	0.0842	0.0842
Sex (female=1)	γ_3	-1.0264	-1.0264	-1.0264
Caucasian/Non-Hispanic (no=1)	γ_4	-0.1422	-0.1422	-0.1422
Tobacco (current or former=1)	γ_5	0.5264	0.5264	0.5264
Diabetes (yes=1)	γ_6	0.3141	0.3141	0.3141
Dyslipidemia (yes=1)	γ_7	0.4122	0.4122	0.4122
Family history of premature (<55 years) Coronary artery disease (yes=1)	γ_8	0.3086	0.3086	0.3086
Hypertension (yes=1)	γ_9	0.4078	0.4078	0.4078

Symptoms unrelated to physical or mental stress (not related=1)	γ_{10}	0.3086	-0.3086	-0.3086
Symptoms unrelated to physical or mental stress (unknown=1)	γ_{11}	-0.195	-0.195	-0.195
HDL (mg/dL)	γ_{12}	-0.00559	-0.318682 HDL constant	-0.252855 HDL constant

Risk groups will be defined as the following:

- Low Risk: Promise Score >0.46
- Elevated Risk: Promise Score ≤ 0.46

Low Risk and Elevated Risk groups are defined using a cut point based on the top 10% of low risk of the PROMISE Risk Score in the PROMISE cohort. Thus, in PRECISE, Low Risk is defined as an absolute score >0.46 .

7. Sample Size and Power Calculations

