9.3.4 Sensitivity Analyses

9.3.4.1 Validation of the Cut Point for PROMISE Risk Score

The prognostic cut point used for the PROMISE risk score will be validated in light of the results of PRECISE. The calibration and discrimination of PROMISE cut points in the PRECISE participant population will be evaluated. Logistic regression model will be used estimate the area under the curve quantified by calculating c-index statistic and mean observed and predicted mean plot. The following lists the outcomes and populations to be evaluated:

- Scenario 1: PRECISE primary endpoint all three components for All Randomized Participants
- Scenario 2: PRECISE primary endpoint two components: Death/MI only for All Randomized Participants
- Scenario 3: Prognostic Value of Risk Score for No CAD + No Event for All Randomized Participants, Only Precision Care Arm Receiving CTA
- Scenario 4: Prognostic Value of Risk Score for Significant or Severe CAD for All Randomized Participants, Only Precision Care Arm Receiving CTA

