Figure 4.5.2	Cumulative Incidence Plot of Non-Cardiovascular Death All Randomized Participants
Table 4.7	Hospitalization Summary
Figure 4.7.1	Cumulative Incidence Plot of Time to 1st CV Hospitalization (CEC) All Randomized Participants
Figure 4.7.2	Cumulative Incidence Plot of Time to 1st Unstable Angina Hospitalization All Randomized Participants
Figure 4.7.3	Cumulative Incidence Plot of Time to 1st Non-CV Hospitalization All Randomized Participants
Table 4.8	Preventive Medication Summary
Table 4.9	Cumulative Radiation Exposure Summary
Figure 4.9.1	Waterfall plot of Cumulate Radiation Exposure
Figure 4.9.2	Waterfall plot of Cumulate Radiation Exposure All Randomized Participants, Excluding Low Risk Participant
Table 4.10	Revascularization Summary
Figure 4.10.1	Cumulative Incidence Plot of 1st Revascularization All Randomized Participants
Table 4.11.1.1	Prevention Motivation Descriptive Summary Day 45 Descriptive Summary
Table 4.11.1.2	Prevention Motivation Descriptive Summary 12 Month Descriptive Summary
Table 4.11.2	Prevention Motivation Testing Results Response at 45 Days All Randomized, As Tested Participants
Table 4.11.4	Prevention Motivation Method of Communication at 45 Days All Randomized, As Tested Participants
Table 4.11.5	Prevention Motivation Association of Method of Communication and Change in Motivation at 45 Days All Randomized Participants, Received Test Results
Table 4.11.6.1	Prevention Motivation Association of Medication Use and Change in Motivation at 45 Days All Randomized Participants
Table 4.11.6.2	Prevention Motivation Association of Medication Use and Change in Motivation at 12 Months All Randomized Participants
Figure 4.12.1.1	Mean observed and predicted mean Prognostic Value of Risk Score PRECISE primary endpoint all three components All Randomized Participants
Table 4.12.1.2	Mean observed and predicted mean Prognostic Value of Risk Score for PRECISE primary endpoint all three components All Randomized Participants
Figure 4.12.2.1	Mean observed and predicted mean

Table/Graph Number	Table/Graph Title
	Prognostic Value of Risk Score PRECISE primary endpoint two components: Death/MI only All Randomized Participants
Table 4.12.2.2	Mean observed and predicted mean Prognostic Value of Risk Score for PRECISE primary endpoint two components: Death/MI only All Randomized Participants

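### The coefficient for symptoms not related to stress (gamma-10) changes sign between the HDL-available and HDL-missing columns of the risk-score table in SAP 6.1, so the score depends on whether HDL was recorded

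*SAP*

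**What the plan says.** SAP 6.1 gives the score as 1/(1+exp(logit)), so a higher logit means a lower score. Scores above 0.46 are low risk. The instruction is "To calculate the PROMISE risk score use the following table estimates based on the risk score paper".

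The table has three columns: HDL available, HDL missing in a woman, and HDL missing in a man. The row "Symptoms unrelated to physical or mental stress (not related=1" holds gamma-10 and reads 0.3086, -0.3086, -0.3086. Every other coefficient except the HDL term is identical across the columns. That includes gamma-11, for the unknown level of the same symptom variable, at -0.195. The equation above the table gives this term without its gamma-10 multiplier.

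Protocol V.A lists the lipid measurements as "high-density lipoprotein [HDL]), if available", so any of the three columns may be needed.

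The score is used in these places:
- SAP 4.2.1 has a subgroup "Above and below PRECISE median score", and a low/elevated subgroup for which "Low Risk is defined as an absolute score >0.46 (see derivation in section 6.1 below".
- SAP 9.3.4.1 says "The calibration and discrimination of PROMISE cut points in the PRECISE participant population will be evaluated".
- SAP 10 plans four figures and four tables for that validation, beginning with "Prognostic Value of Risk Score PRECISE primary endpoint all three components".

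**The concern.** The columns for missing HDL should differ from the first column only in the HDL term. As printed, the symptom effect also reverses. Among participants with HDL recorded, being in the not-related category lowers the score relative to the related category. Among those with HDL missing, it raises the score. Nothing in either document explains a symptom effect that depends on whether a laboratory value is on file.

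An analyst who follows the table would score the same symptom history in two opposite ways. The validation of the cut point is the most exposed analysis, because calibration and discrimination would be computed on a score that mixes the two rules. The median split would also use that mixed score. The low/elevated subgroup is affected only if it is re-derived from the score rather than taken from the randomisation stratum.

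**Working it through.** **Inputs, all from SAP 6.1.** Intercept -3.7524; age 0.0842 per year; female -1.0264; dyslipidemia 0.4122; gamma-10 +0.3086 or -0.3086; gamma-11 -0.195; HDL slope -0.00559 per mg/dL; HDL constants -0.318682 (women) and -0.252855 (men); cut point 0.46.

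**1. Are the columns one model?** Divide each HDL constant by the slope.
- Women: -0.318682 / -0.00559 = 57.0 mg/dL.
- Men: -0.252855 / -0.00559 = 45.2 mg/dL.

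The columns for missing HDL are therefore the first column with a fixed sex-specific HDL put in. As a control, take a 52-year-old white non-Hispanic woman without the not-related indicator or any other risk indicator. She scores 0.672 whether HDL is recorded at 57.0 or missing. The discrepancy comes from gamma-10 alone.

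**2. Size of the conflict at the substituted HDL.**
- Logit gap: 0.3086 - (-0.3086) = 0.6172.
- Odds factor: exp(0.6172) = 1.85.
- In years of age: 0.6172 / 0.0842 = 7.3.
- In HDL: 0.6172 / 0.00559 = 110.4 mg/dL. To cancel the gap, a recorded HDL would have to be 57.0 + 110.4 = 167.4 mg/dL in a woman or 45.2 + 110.4 = 155.6 mg/dL in a man.
- Not related minus unknown: 0.3086 + 0.195 = +0.5036 with HDL recorded, and -0.3086 + 0.195 = -0.1136 with HDL missing.

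**3. Can it change the risk group?** The logit at the cut point is ln(0.54/0.46) = 0.1603. Take a white non-Hispanic woman aged 58 with symptoms not related to stress and dyslipidemia as her only risk factor. Before the symptom and HDL terms, her logit is -3.7524 + 0.0842 × 58 - 1.0264 + 0.4122 = 0.5170.

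| gamma-10 | HDL 35 | HDL 57 | HDL 100 | HDL missing |
|---|---|---|---|---|
| As printed | 0.348 | 0.376 | 0.434 | 0.528 |
| Positive in all columns | 0.348 | 0.376 | 0.434 | 0.376 |
| Negative in all columns | 0.497 | 0.528 | 0.587 | 0.528 |

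As printed she is elevated risk at each of these recorded HDL values and low risk if HDL is missing. To be low risk with HDL recorded she would need more than (0.5170 + 0.3086 - 0.1603) / 0.00559 = 119.0 mg/dL. Under either single sign her group is the same throughout: elevated if positive, low if negative.

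The same happens with no other risk indicator and HDL at the substituted value. A woman aged 60 scores 0.435 with HDL recorded and 0.588 with it missing. A man aged 50 scores 0.374 and 0.526.

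**4. Does the equation settle it?** No. Without its multiplier the term would carry a coefficient of 1, which is neither printed value.

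**The case against.** The strongest objection is that the plus sign may not be in the SAP at all. The copy reviewed is text extracted from PDF. The cell is the first one after a break in the table, and a cell in the next table (SAP 7, Table 1) is visibly garbled. Against that, all 17 other negative entries in the table kept their sign, five of them in the same column and two in the same row. A lost minus sign is therefore less likely but not excluded. The missing multiplier carries the same doubt.

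The second objection is reach. Protocol IV.G says every participant is scored by the risk calculator during randomisation. The documents do not show that this code used a wrong coefficient, nor whether analysts will reuse a stored score. The primary log-rank test does not use the score, and it is not among the adjusted Cox covariates in SAP 9.2. Analyses defined by randomisation stratum are not shown to be affected, and nor is the power. Participants with known non-obstructive disease cannot change stratum, because SAP 6 says "participants with known non-obstructive coronary atherosclerosis or plaque will be assigned to the elevated risk strata regardless of risk score". The score uses baseline data only, so an error would regroup both arms by the same rule, and the randomised comparison within a median-split subgroup would stay intact.

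These limits stand. They do not remove the problem, because SAP 6.1 directs the analyst to calculate from this table, and the median split and the cut-point validation need the numeric score.

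**Conclusion.** The concern holds. As the table reads, gamma-10 has opposite signs in columns that are otherwise one model, and at most one sign can be right. At the substituted HDL the inconsistency is 0.6172 logits, large enough to reverse the risk group of participants near the cut point. It bears on the median-split subgroup and the eight planned validation outputs, and on the low/elevated subgroup only if that is re-derived.

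Confidence is medium, because a sign lost in extraction remains possible. The documents do not settle which sign is right. They also do not give the share of participants with symptoms not related to stress or the share with missing HDL, so the number affected cannot be estimated. The worked profiles show that the risk group can change, not how often it does.

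**What to change.** 1. Check the gamma-10 row and the equation on the original page of SAP 6.1. If the page shows one sign in all three columns, the only correction needed is the multiplier, if that is missing there too.
2. Otherwise, reconcile both the sign and the value of gamma-10 with the cited source model and with the risk calculator and IXRS code. The value needs checking as well because its absolute size, 0.3086, equals gamma-8 (family history). Print one value in all three columns and put the gamma-10 multiplier in the equation.
3. Use the reconciled score for the median split and the cut-point validation.
4. As a programming check, cross-tabulate the re-derived risk group against the IXRS stratum. Participants placed in the elevated stratum for known atherosclerosis will differ by design.

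The cost is one look at the page, one table row, one term in the equation and one cross-tabulation.

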	
 3. Noninvasive or invasive CV testing for CAD within 1 year. CV testing for CAD refers to any stress tests, invasive coronary angiography (ICA) and cCTA (including calcium scoring) only. 
 a. Resting ECG, resting echocardiogram and resting CMR (MRI) are not exclusionary regardless of when were performed 4. Lifetime history of known obstructive CAD (prior myocardial infarction, CABG or PCI, stenosis $\geq 50\%$), known EF $\leq 40\%$ or other moderate to severe valvular or congenital cardiac disease 5. Contraindications to cCTA including but not limited to creatinine clearance (GFR) < 45 ml/min as per most recent measurement taken within 90 days 6. Exceeds the site's weight or size limit for cCTA or cardiac catheterization 7. Any condition leading to possible inability to comply with the protocol procedures or follow-up 8. Any condition that might interfere with the study procedures or follow-up 9. Enrolled in an investigational trial that involves a non-approved cardiac drug or device which has not reached its primary endpoint 10. Life expectancy less than 2 years due to non-cardiovascular comorbidities
Study Follow-up	Participant follow-up will be done at 45 days, 6 months, and 1 year.
Sample Size Considerations	
Primary superiority testing hypothesis of all cause death/MI or invasive cardiac catheterization without obstructive CAD (diameter stenosis $\geq 50\%$ or $FFR \leq 0.80$ or $iFR \leq 0.89$) at one year (intention to treat, time to first event analysis): Assuming an 8% event rate at 1 year in the usual care group and 5% in the precision care group (3% absolute [37.5% relative] effect magnitude). Assumed rates are based on estimated ~20% assigned to guideline-recommended care with symptom management and no planned testing (within which 30% will cross over to cCTA with selective FFR_{CT}); and overall 10% will not receive assigned testing; enrolling 1050 participants per group (2100 total participants) would provide at least 90% power to demonstrate superiority accounting for 10% attrition rate.

II. INTRODUCTION

II.A. Primary Hypotheses

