Diagnostic testing for the assessment of CAD symptoms is ordered by physicians and other clinicians from many specialties and is performed in multiple settings, including physician offices, hospital outpatient departments, and diagnostic testing facilities. A trial, such as PRECISE, that seeks to improve the management of non-ACS chest pain must incorporate this diversity in order to be broadly relevant to the target population under study. PRECISE site selection will seek to encompass this diversity.

Study duration

The anticipated total duration of the PRECISE study will be approximately 36 months for start-up, enrollment, follow up, and close out. Participants will be followed for 12 months after enrollment.

Study design

The figure below represents a diagrammatic representation of the trial design.

IV.B. Primary Objective and Endpoints

The primary objective of the PRECISE study is to assess clinical outcomes, patient-reported outcomes, decision making regarding noninvasive testing and invasive angiography, and costs using a precision evaluation strategy as compared to a usual care strategy in participants with stable symptoms suggestive of significant coronary artery disease. The precision evaluation strategy will be based on a pre-test risk assessment which will be used to assign participants to either cCTA with selective FFR_{CT} or guideline-recommended care with symptom and risk factor management and no immediately planned testing. In addition, patients with known mild coronary plaque without obstructive stenosis or extensive coronary calcium randomized to the precision evaluation arm are mandated to undergo cCTA +/- FFR_{CT}, independent of their PROMISE risk score strata. We hypothesize that in stable patients with a clinical recommendation for testing to evaluate suspected significant CAD, the proposed precision evaluation strategy will improve outcomes and reduce costs compared to usual care evaluation.

The primary endpoint is a composite of: MACE (all cause death and non-fatal MI) or invasive cardiac catheterization without CAD (no coronary stenosis \geq 50% according to QCA by core-lab adjudication or site interpretation if QCA is not available, or with FFR \leq 0.80, instantaneous wave free ratio (iFR) \leq 0.89) or other validated NHPR. The primary study hypothesis will be tested at one

year using an intention to treat analysis.

IV.C. Secondary Endpoints

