Sample size and power calculations for this study are based on the hypothesis that the precision evaluation arm is superior to the usual care arm on the time-to-first event of the composite MACE endpoint (defined as: all-cause death, non-fatal MI) or invasive cardiac catheterization without obstructive CAD (obstructive CAD defined as diameter -stenosis $\geq 50\%$, $FFR \leq 0.80$ or $iFR \leq 0.89$). Time to event analysis will use the date of the event, including the date of catheterization which is used to determine the absence of obstructive CAD. Assuming 10% of usual care participants will receive angiography as a first test results in an 8% primary endpoint event rate at 1 year in the usual care group and 5% (absolute) event rate in the precision care group (i.e., 37.5% relative effect size) with an estimated ~20% assigned to guideline-recommended care with symptom management and no planned testing. Assumptions used in the primary endpoint event rate calculations (i.e. 8% vs. 5%) were: an overall ~10% will not receive randomized testing and within the precision evaluation arm, 30% of those assigned to guideline-recommended care will cross over to cCTA with selective FFR_{CT} .

Enrolling 1050 patients per group (2100 total participants) would provide at least 90% power to detect a relative risk reduction of 37.5% in the precision evaluation arm. Sample size calculations are based on the log-rank test⁵² with 12-month accrual period, a 12-month follow-up in all participants, 10% attrition rate (i.e., lost to follow-up, dropouts) and a two-sided type I error rate of 0.05.

1-yr event rate in precision evaluation arm	Power	Total number of participants needed	Total number of cath and MACE needed
5% (37.5% effect size)	85%	1792	173
	90%	2096	202
	95%	2592	250

Table shows total number of participants needed for 85%, 90% and 95% power. Although, this is not an event-driven study, the table also provides total number of cath and MACE needed.

Power curves (**Figure: Long-Rank for Two Survival Curves**) provide total sample size needed for several relative effect size (i.e., 1-hazard ratio) scenarios.

[figure not shown]

Figure: Long-Rank for Two Survival Curves

VIII.B. Statistical Analysis Plan

Analysis of the Primary Endpoint

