Sample size and power calculations for this study are based on the hypothesis that the precision evaluation arm is superior to the usual care arm on the time-to-first event of the composite 3-component endpoint: all-cause death, non-fatal MI, or invasive cardiac catheterization without obstructive CAD (obstructive CAD defined as diameter stenosis $\geq 50\%$, FFR ≤ 0.80 , or iFR ≤ 0.89) over a 12-month of follow-up. Time to event analysis will use the date of the event, including the date of catheterization at which the absence of obstructive CAD is demonstrated. Assuming 10% of usual care participants will receive angiography as a first test results in an 8% primary endpoint event rate at 1 year in the usual care group and 5% event rate in the precision care group (i.e., 3% absolute [37.5% relative] effect size). Assumptions used in the primary endpoint event rate calculations (i.e., 8% vs. 5%) were: overall 10% will not receive randomized evaluation, and within the precision evaluation arm, approximately 20% will be assigned to guideline-recommended care with symptom management and no planned testing, of whom about 30% will have escalation of care to cCTA with selective FFRCT.

Randomizing 1050 participants per group (2100 total participants) is estimated to provide at least 90% power to detect a relative risk reduction of 37.5% in the precision evaluation arm (see Table 1 below, or refer to the power curves in the protocol). Sample size/power calculations are based on the log-rank test with 12-month accrual period, a minimum 12-month follow-up (i.e. last participant will be followed for at least 12-months), 10% attrition rate (i.e. lost to follow-up, dropouts) and a two-sided type I error rate of 0.05.

The DSMB will review interim analysis data for efficacy as well as possible sample size re-estimation. At any interim analyses, the O'Brien-Fleming boundary generated by Lan-DeMets alpha-spending function will be utilized as a statistical stopping rule (See DSMB charter for more details).

Table 1. The total number of participants needed for 85%, 90%, and 95% power. Although this is not an event-driven study, the table below also provides total number of MACE needed.

1-year event rate in precision evaluation arm	Power	Total number of Primary Events needed	Total number of participants needed
(37.5% ^{2%} effect size)	85%	173	1792
	90%	202	2096
	95%	250	2592

8. Database Sources

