9.2 Primary Efficacy Analysis

The primary endpoint of this study is estimated as time to first occurrence of any of its three following components:

- All-cause death
- Non-fatal MI
- Invasive cardiac catheterization without obstructive CAD

Each death will be adjudicated for cause and date by the CEC. Potential MI cases will be adjudicated for MI yes/no, fatal/non-fatal, MI type, and date of MI by the CEC. Cath without obstructive CAD is the absence of obstructive CAD, defined as diameter stenosis $\geq 50\%$ in a vessel ≥ 2 mm both assessed by QCA (or site read if QCA is not available), $FFR \leq 0.80$, or $iFR \leq 0.89$. The catheterization component of the primary endpoint will be determined according to the algorithm diagrammed below:

To derive the catheterization component of the primary endpoint, site, core lab and DCRI entered clinical data present in the clinical EDC will be extracted and processed through a HeartFlow Cath Algorithm to be classified as Obstructive CAD, No Obstructive CAD, Indeterminate, or Incomplete data. Each ICA classified as either Obstructive CAD, No Obstructive CAD, or Indeterminate will undergo individual Medical Monitor review. For ICAs receiving a final classification as confirmed Obstructive CAD or No Obstructive CAD, the results are considered final. For ICAs confirmed by the Medical Monitor as Indeterminate or ambiguous, CEC adjudication will make the final determination. Incomplete ICAs will be reprocessed through the Cath Algorithm once data are complete and query free.

The time from randomization to the first event among the components of the primary endpoint will be measured (in days) for those who experienced an event and calculated as the date of the first event minus the date of randomization + 1. For participants who do not experience any of the primary component events or who withdraw consent or drop out of the study before experiencing an event, time from randomization to the date of last contact + 1 will be used in the analysis, and those participants will be considered as censored observations in the time-to-event analysis. The 12-month analysis will be censored at 395 days (365 days + 30 day visit window) such that only events on or before this time will be counted in the analysis and event free participants with follow-up greater than 395 will be set to 395.

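### The stated 90% power and 202 events assume 12 to 24 months of follow-up; the 12-month primary analysis (cut at day 395) gives about 130 to 148 events and 75 to 84% power

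*SAP*

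**What the plan says.** SAP section 7 gives the design as 8% versus 5% at one year, log-rank test, two-sided 0.05, and says "Randomizing 1050 participants per group (2100 total participants) is estimated to provide at least 90% power to detect a relative risk reduction of 37.5"%. Its Table 1 lists 173, 202 and 250 events for 1792, 2096 and 2592 participants at 85%, 90% and 95% power.

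The documents describe the follow-up behind these figures in different ways:

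- SAP section 7 defines the endpoint "over a 12-month of follow-up. Time to event analysis will use the date of the event".
- The same section bases the power calculation on 12-month accrual and "a minimum 12-month follow-up (i.e. last participant will be followed for at least 12-months), 10% attrition rate".
- SAP section 4.1 limits the endpoint to 365 ± 30 days, and section 9.2 says "The 12-month analysis will be censored at 395 days (365 days + 30 day visit window"). Later events are not counted.
- The final protocol, IV.A Study duration, says "Participants will be followed for 12 months after enrollment". Its section VIII.A describes the calculation "with 12-month accrual period, a 12-month follow-up in all participants, 10% attrition rate", yet prints the same participant and event numbers.
- The final protocol's synopsis repeats that the sample "would provide at least 90% power to demonstrate superiority accounting for 10% attrition rate".

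The original protocol, which planned 24 months of follow-up, has the identical table. SAP section 11 lists only the added day in the time-to-event formula as a change from the protocol.

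**The concern.** The follow-up was shortened but the table was not recalculated. In every row of Table 1 the events are about 9.6% of the participants (202/2096 = 9.64%). The assumed 12-month rates are 8% and 5%, which average 6.5%. A pooled proportion of 9.6% exceeds even the higher arm's 12-month rate, so it cannot come from a 12-month window.

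The planned power of the primary test is therefore overstated, and a neutral result would be read as coming from a trial with 90% power. SAP section 7 also says "The DSMB will review interim analysis data for efficacy as well as possible sample size re-estimation". Any re-estimation that starts from 202 events and 90% power starts from figures that the planned analysis cannot deliver.

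**Working it through.** **Inputs.** From SAP section 7: 8% and 5% at one year, 1:1 allocation, 1050 per arm, two-sided 0.05, 10% attrition. From SAP section 9.2: cut at day 395. The plan does not say how attrition is modelled; exponential loss at 10% per year is assumed here because it reproduces the stated sample sizes. No-loss figures are also shown.

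**Formulas.**

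- Hazards: −ln 0.92 = 0.0834 and −ln 0.95 = 0.0513 per year, so HR = 0.615. HR 0.625 applies if the 37.5% reduction is read as a hazard reduction.
- Loss hazard: θ = −ln 0.90 = 0.1054 per year.
- Probability of an observed event by time T: λ/(λ+θ) × [1 − exp(−(λ+θ)T)].
- Power with D events: Φ(√D × (1−HR)/(1+HR) − 1.96) (Freedman), or Φ(√D × |ln HR|/2 − 1.96) (Schoenfeld).

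**Step 1: reproduce the table.** Let T be uniform on 1 to 2 years (12-month accrual plus a 12-month minimum), with loss and HR 0.615. The event probabilities are 10.84% and 6.83%, mean 8.84%. At N = 2096 this gives 185.2 events, and Freedman power is Φ(13.61 × 0.2383 − 1.96) = Φ(1.28) = 0.900. The three rows, N = 1792, 2096 and 2592, give 0.850, 0.900 and 0.950. The table's sample sizes therefore fit the 12-to-24-month design.

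The event column appears to be on another basis. With loss, the same design gives 158–159, 185–186 and 229–230 events. Without loss it gives 171–172, 200–202 and 248–249, close to the stated 173, 202 and 250.

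**Step 2: expected events by month 12.** Without loss: 1050 × 0.08 + 1050 × 0.05 = 84 + 52.5 = 136.5. This needs no assumption about the shape of the hazard.

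**Step 3: power for the window analysed, N = 2100.** Example, day 365 with loss, HR 0.615: the probabilities are 7.60% and 4.75%, mean 6.17%, so D = 129.6. Freedman: Φ(11.38 × 0.2383 − 1.96) = 0.774. Schoenfeld: Φ(11.38 × 0.2429 − 1.96) = 0.790.

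| Cut-off | Loss | Events | Power, HR 0.615 | Power, HR 0.625 |
|---|---|---|---|---|
| Day 365 | none | 136.5–137.3 | 79.5–81.0% | 77.2–78.6% |
| Day 365 | 10%/year | 129.6–130.4 | 77.4–79.0% | 75.0–76.5% |
| Day 395 | none | 147.3–148.2 | 82.4–83.9% | 80.2–81.6% |
| Day 395 | 10%/year | 139.3–140.1 | 80.3–81.8% | 78.0–79.5% |

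Each power range runs from Freedman to Schoenfeld; each event range covers the two hazard ratios.

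**Step 4: simulation.** Log-rank power at HR 0.615 (8000 runs), without and with loss, was 80.6% and 77.3% at day 365, and 82.7% and 80.4% at day 395. The 12-to-24-month design with loss gave 90.6%.

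**Step 5: other readings tried.** A two-proportion test gives 79.7% power with 1050 per arm and 75.4% with 945 per arm. One-sided 0.05 reaches 90% at 147 events, but the SAP specifies a two-sided test and 202 events would still not arise.

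**The case against.** The 12-month event count cannot be disputed, but several qualifications can be raised.

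- **The exact match depends on one combination** (Freedman, HR 0.615, exponential loss). Schoenfeld with the same inputs gives 86.4%, 91.1% and 95.7%. This is true, but either formula puts the stated sample sizes near their stated power only with 12 to 24 months of follow-up.
- **The event-column explanation is inference about software output.** The closest no-loss match needs HR 0.625, while the sample sizes fit HR 0.615. This stands: treat that part as a likely explanation. The main point does not need it.
- **The overall range mixes scenarios.** The 84% end ignores attrition, and the 75% end needs HR 0.625 with Freedman. With attrition and HR 0.615 the range is 77 to 82%. Nor is 75% a floor: if 10% of participants contributed nothing, about 123 events would accrue by day 365, with 75 to 77% power at HR 0.615.
- **The day-395 figures assume a constant hazard.** Initial tests are due before the 45-day visit, so catheterizations may cluster early. The extra 30 days would then add fewer events than shown.
- **The trial is not event-driven, and type I error and the effect estimate are unaffected.** This is correct. The error lies in the stated power and event count.

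**Conclusion.** The power statement is wrong as written. Power of 90% and 202 events belong to a design with 12 to 24 months of follow-up per participant, which the primary analysis does not use. For 8% versus 5% with 2100 participants, expect about 130 to 137 events and 75 to 81% power at day 365, or 139 to 148 events and 78 to 84% at day 395. The chance of missing the design effect is about 16 to 25%. Even with no loss and the more favourable formula, power reaches only 84%.

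The 136.5 events at month 12 rest only on the plan's rates and sample size. The other figures assume constant hazards and the stated loss model. Alpha spent at interim analyses would lower power slightly, by about 1 point if the final level were 0.0455 (an assumed value).

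**What to change.** In SAP section 7, Protocol VIII.A and the Protocol synopsis:

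1. Recompute the table for the fixed 12-month/day-395 window with 10% attrition, putting participants, power and events on the same attrition basis, and state how attrition is modelled.
2. State about 130 (day 365) to 140 (day 395) expected events and about 75 to 82% power for 8% versus 5%. Alternatively, state that 90% power applies to a relative reduction of about 42 to 44% (4.5 to 4.7% in the precision arm), and say whether that effect is plausible.
3. Replace the minimum-follow-up wording in the SAP with the final protocol's 12 months for all participants.
4. For any sample size re-estimation, record the number that would keep 90% power for 8% versus 5%. With 10% yearly loss and HR 0.615 this is about 2,680 to 2,790 participants at day 395, or 2,880 to 3,000 at day 365.
5. If the DSMB charter, which was not available for this review, takes 202 events as full information, update it. Otherwise the final analysis would fall at about 130/202 = 64% to 140/202 = 69% of nominal information.

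The cost is one recomputed table and some wording. The stated power becomes less favourable, but correcting it requires no extra participants and no change to the endpoint or test.
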